- l. On Day 1, ASQ will be completed predose (within 60 minutes prior to dosing) and approximately 10 minutes (+15 minutes), 1 hour (+15 minutes), and 2 hours (+15 minutes) postdose. This assessment will be performed after completion of all other simultaneously scheduled procedures to avoid interference with scheduled vital sign, ECG, and PK evaluation (see [Section 8.2.4](#)).
- m. All SAEs will be collected from the signing of the ICF until the last study visit at the timepoints specified in the SoA. All AEs will be collected from the start of study treatment until the last study visit at the timepoints specified in the SoA.
- n. Study Treatment will be administered on Day 1 in the morning after at least a 10 hour overnight fast with an approximately 4 hour fast following dose administration. Note: All scheduled postdose assessments listed in [Table 1](#) and [Table 2](#) are relative to the start of the IV infusion.
- o. PK blood and urine collection timepoints (see [Table 2](#)).

Table 4 Detailed Schedule of PK, Urine, dECG, Safety ECG, ASQ, Injection Site Assessment and Vital Signs During Single IV Administration Days -1 to Day 3

Day	Time Relative to IV Infusion Dose (T=0) ^a and PK windows	Time relative to End of Infusion ^b (EOI)	PK Blood ^b	Urine ^c	dECG ^d and Safety ECG ^e (triplicates)	Vital Signs ^f	ASQ ^g	Injection Site Assessment ^h
Admission/ Day -1	4 hour Holter*				X^{d,e} (4 hour Holter)	X^f	X	
Day 1	Predose (within 60 minutes of dose)	Predose	X (Within 60 mins of start of infusion)		-12 to 0 hr (±15 min)	X^{d,e} (Holter to start approx. 60 mins before start of infusion)	X (within 60 mins of start of infusion)	X (within 60 mins of start of infusion)
		5 minutes into Infusion				X^j (±2.5 min)		
	End of IV infusion (+1 minute)	At End of Infusion (EOI)	Xⁱ (+1 min)			X^j (1 to 4 min post EOI)		X (+15 min)
	15 min (+1 minutes)	5 minutes	Xⁱ (+1 min)					
	20 min (+1 minutes)	10 minutes	Xⁱ (±1 min)					
	30 min (+2 minutes)	20 minutes	Xⁱ (±2 min)					
	40 min (+2 minutes)	30 minutes	Xⁱ (±2 min)					
	50 min (+4 minutes)	40 minutes	Xⁱ (±4 min)					
	1 hr, 10 minutes (+4 minutes)	1 hr	Xⁱ (±4 min)					
	1 hour, 40 minutes (+10 minutes)	1.5 hr	Xⁱ (±10 min)					
	2 hr, 10 minutes (+10 minutes)	2 hr	Xⁱ (±10 min)					
	2 hr, 40 minutes (+10 minutes)	2.5 hr	Xⁱ (±10 min)					
	2 hr, 10 minutes (+10 minutes)	3 hr	Xⁱ (±10 min)		2 to 4 hr (±15 min)	X^e (±10 min)	X (±10 min)	X (+15 min)
	4 hr (+15 minutes)	4 hr	X (±15 min)					X (+15 min)

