	5 hr (+15 minutes)	5 hr			4 to 6 hr (±15 min)			X (+15 min)
	6 hr (+15 minutes)	6 hr	X (±15 min)			X^e (±10 min)	X (±10 min)	X (+15 min)
	8 hr (+15 minutes)	8 hr	X (±15 min)		6 to 12 hr (±15 min)	X^e (±10 min)	X (±10 min)	
	12 hr (+15 minutes)	12 hr	X (±15 min)					
Day 2	24 hr (+30 minutes)	24 hr	X (±30 min)	12 to 24 hr (±15 min)	X^{d,e} (Holter to end after 24-hr)	X (±10 min)		X (+12 hr)
	36 hr (+30 minutes)	36 hr	X (±30 min)	24 to 36 hr (±15 min)		X (±10 min)		
Day 3	48 hr (+30 minutes)	48 hr	X (±30 min)	36 to 48 hr (±15 min)	X^e (±10 min)	X (±10 min)		X (any time prior to discharge)

Abbreviations: ASQ: Anxiety Symptoms Questionnaire; CRU = clinical research unit; dECG: Digital electrocardiogram; EOI = end of infusion; hr = hour; IV = intravenous; min = minutes; PK: pharmacokinetics; (T=0) = Time equals 0.

* Continuous Holter performed during the day of admission

- a. All predose procedures and PK blood samples may be taken up to 60 minutes prior to start of the 10 minute IV infusion on Day 1. All postdose procedures and PK blood samples will be collected relative to the end of the IV infusion unless otherwise indicated or there is a significant extension of the infusion duration (see footnote ^b below).
- b. The following windows will be allowable for PK samples: a ±1 minute window will be allowed for samples taken up to and including 10 minutes postdose, a ±2 minute window will be allowed for samples at 20 and 30 minutes postdose, a ±4 minute window will be allowed for samples at 40 minutes, 50 minutes, and 1 hour postdose, a ±10 minute window for samples taken between 1.5 hours and 3 hours postdose; a ±15 minute window is acceptable for samples taken at >3 hours postdose, and a ±30 minute window is acceptable for samples taken at >12 hours postdose.
- c. A small amount of urine will be removed at each interval for urinalysis. Removal of urine will occur after the volume of the pooled urine has been recorded.
- d. ECGs to be extracted from the continuous Holter on Days 1 and 2 as listed in [Table 2](#) and will be time-matched with PK sample collections from predose to 24-hour postdose. Digital ECG assessments will be extracted at a time prior to the PK sample collection. Participants will remain in supine position for at least 5 minutes before each of the planned ECG extraction.

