8.0 STUDY ASSESSMENTS AND PROCEDURES

- Study procedures and their timing are summarized in the SoA ([Section 1.3](#)). Protocol waivers or exemptions are not allowed.
- Immediate safety concerns should be discussed with the Sponsor immediately upon occurrence or awareness to determine if the participant should continue or discontinue study treatment.
- Adherence to the study design requirements, including those specified in the SoA ([Section 1.3](#)), is essential and required for study conduct.
- All screening evaluations must be completed and reviewed to confirm that potential participants meet all eligibility criteria. The Investigator will maintain a screening log to record details of all participants screened and to confirm eligibility or record reasons for screening failure, as applicable.
- Procedures conducted as part of the participant's routine clinical management (e.g., blood count) and obtained before signing of the informed consent form (ICF) may be utilized for screening or baseline purposes provided the procedures met the protocol-specified criteria and were performed within the timeframe defined in the SoA ([Section 1.3](#)).

The maximum amount of blood collected from each participant over the duration of the study, including any extra assessments that may be required, will not exceed 450 mL.

Repeat or unscheduled samples may be taken for safety reasons or for technical issues with the samples.

When multiple procedures are scheduled at the same visit, the order of assessments will be, ECG procedures, vital signs, PK sample collection (nominal), questionnaire, and injection site assessment. All scheduled postdose times listed for the assessments in the SoA ([Section 1.3](#)) are relative to the start of the IV infusion unless there is a significant extension of the infusion duration or infusion interruption (see [Table 2](#)).

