Continuous 24-hour Holter-ECG monitoring will be performed as outlined in the SoA [Section 1.3](#). The ECGs will be extracted from Holter at predefined timepoints to be time-matched with PK samples as detailed in [Table 1](#) and [Table 2](#), [Section 1.3](#).

Date and time of intake (start and completion) of any food during the Holter-ECG recording period will be recorded on the source documents and eCRF.

All ECGs for QT evaluation will be recorded by using high resolution (1,000 Hz) 12-lead digital Holter recorders provided by the ECG central laboratory. All Holter recording relevant procedures will be described in a manual provided by the central laboratory.

The CRU staff involved in the recording of the Holter ECGs will receive a training comprising study participant preparation, electrode placement, recording of the Holter-ECG under resting conditions, and data upload from the Holter-ECG recorded.

The same recorder/model will be used for all recordings for a study participant. Prior to each recording, the Holter recorder should be loaded with fresh batteries. The date and time settings must be checked at the start of each study day and synchronized with an official timekeeper for all machines used in the study.

Skin preparation must be thorough and electrode positions must be according to electrode positions recommended by the Laboratory Manual. Electrode positions will be marked with an indelible pen at the start of the study day to ensure exact reposition.

The 12-lead dECGs for concentration QTcF analysis will be extracted by the designated central laboratory after the study participant has remained in the supine position for at least 5 minutes.

TriPLICATE 12-lead dECGs for safety monitoring will be extracted within a 5-minute window preceding and up to the specified ECG acquisition time point.

Prior to conducting the concentration-QT analysis, a separate analysis plan will be prepared detailing the procedure and analysis.

During extraction periods on days when dECG Holter measurements are being taken, study participants should be restricted to a low level of physical activity and should refrain from any activities likely to stimulate or excite them as outlined in [Section 5.3.3](#) due to potential interference with ECG signals. Food and drink should be restricted as detailed in the protocol (see [Section 5.3.1](#)) as this also has the potential to affect ECG signals.

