8.4.3 Calculation of Derivation of Pharmacokinetic Variables

Pharmacokinetic parameters will be derived using noncompartmental methods with Phoenix® WinNonlin® Version 8.3 or higher (Certara, L.P. Princeton, New Jersey, United States of America [USA]) and/or SAS® Version 9.4 or higher (SAS Institute, Inc., Cary, North Carolina, USA). Actual elapsed time from start of the IV infusion will be used for the final plasma PK parameter calculations. Nominal time from end of the IV infusion will be used for preliminary PK parameter calculations.

The plasma PK parameters in Table 4 will be determined for CS-1103. A minimum of 3 quantifiable postdose concentrations will be required for all calculations.

Table 6 Plasma Pharmacokinetic Parameters

Pharmacokinetic Parameter	Definition
C_{\max}	Maximum concentration, obtained directly from the observed concentration versus time data
C_{EOI}	Concentration at the end of the 10-minute IV infusion
t_{\max}	Time to C_{\max}
$AUC_{(0-\infty)}$	Area under the plasma concentration-time curve from time zero extrapolated to infinity, calculated by linear up/log down trapezoidal summation
$AUC_{(0-\text{last})}$	Area under the plasma concentration-time curve from time zero to the time of the last quantifiable concentration, calculated by linear up/log down trapezoidal summation
CL	Systemic clearance

V_z	Volume of distribution
V_{ss}	Steady-state volume of distribution
$t_{1/2}$	Half-life; a minimum of 3 points will be used for estimation
λ_z	Elimination rate constant

Abbreviation: IV = intravenous.

Note: No dose correction for the sodium salt will be required for dose-dependent parameters, as both CS-1103 dose and plasma concentrations will be based on the weight of the tetrasodium salt.

For this study, an extrapolation of 30% will be considered acceptable for considering $AUC_{(0-\infty)}$ sufficiently well defined. Dose normalized exposure will also be determined. Additional plasma parameters may be calculated if deemed appropriate. Further details with respect to the PK analysis will be provided in the statistical analysis plan (SAP).

Any preliminary plasma PK result for use by the SRC will be reported in a manner that maintains blinding of the treatment the participants have received unless otherwise requested by the SRC. The urine PK parameters in Table 5 will be determined for CS-1103.

Table 7 Urine Pharmacokinetic Parameters

Pharmacokinetic Parameter	Definition

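### The protocol gives two different windows for the end-of-infusion blood sample: +1 minute in the Table 2 row, ±1 minute in footnote b, so a draw one minute before the infusion ends complies with the footnote

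*Protocol*

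**What the plan says.** **Blood sample.** In Table 2 of Protocol Section 1.3, the label of the EOI row begins "End of IV infusion (+1 minute", and the PK blood cell of that row repeats +1 min. Footnote b to the same table says "a ±1 minute window will be allowed for samples taken up to and including 10 minutes postdose". Neither text says which governs.

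**Parameter.** Protocol Section 8.4.3 defines C_EOI as "Concentration at the end of the 10-minute IV infusion". Cmax is the highest observed value. Both are listed secondary endpoints, and Cmax enters the power model in SAP Section 15.2.

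**Clock.** SAP Section 15.2 computes parameters from actual time elapsed since the end of infusion. Protocol Section 8.4.3 counts actual time from the start of infusion for the final parameters.

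**ECG.** Footnote d says that the ECGs taken from the Holter recording "will be time-matched with PK sample collections from predose to 24-hour postdose", and adds: "Digital ECG assessments will be extracted at a time prior to the PK sample collection". Section 8.0 gives the same sequence: "the order of assessments will be, ECG procedures, vital signs, PK sample collection (nominal), questionnaire, and injection site assessment". The only numerical extraction window is in Section 8.2.3.2. It is stated for the safety digital ECGs, which "will be extracted within a 5-minute window preceding and up to the specified ECG acquisition time point". The sentence on the QT-analysis ECGs ("The 12-lead dECGs for concentration QTcF analysis will be extracted by the designated central laboratory") adds only a supine rest of at least five minutes. Both documents defer the concentration-QT analysis to a separate plan.

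**The concern.** A window that is harmless elsewhere in the profile matters at the end of a short infusion. Before the pump stops the concentration is rising steeply, and a minute is a tenth of the whole input. A sample drawn early is not the quantity that C_EOI names, and the error goes one way only, downward. If the site follows the footnote, some participants have an end-of-infusion value and others a value from during the infusion, under one label and with no protocol deviation recorded. The SAP has no rule for a post-start sample that falls before its time zero.

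The same geometry applies to an ECG taken before the EOI sample: its QTcF would belong to a lower concentration than the one it is paired with.

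**Working it through.** **1. Does footnote b reach the EOI sample?** Counted from the end of infusion, the sample is at 0 minutes; counted from the start, at 10 minutes. Both lie within the range up to and including 10 minutes. So footnote b applies on either clock and allows minutes 9 to 11, while the row allows minutes 10 to 11.

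**2. Profiles.** The documents give no figure for this error, so there is none to reproduce. The protocol's footnote on the 40 mg/kg dose (Section 4.5) projects C0 = 340 µg/mL and AUC(0-last) = 318 µg·h/mL. Per mg/kg these are 340/40 = 8.5 and 318/40 = 7.95. I treat them as the intercept and total area of the curve after an instantaneous dose and apply a 10-minute constant-rate infusion.

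For a disposition curve Σ wᵢ·exp(−kᵢt), with T = 1/6 h, the concentration is proportional to:
- for t ≤ T: Σ (wᵢ/kᵢ)·(1 − exp(−kᵢt))
- for t > T: Σ (wᵢ/kᵢ)·(1 − exp(−kᵢT))·exp(−kᵢ(t − T))

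The constraints are Σ wᵢ = 8.5 and Σ wᵢ/kᵢ = 7.95. Three profiles meet them:
- **A**, one exponential: k = 340/318 = 1.069/h, half-life 0.65 h.
- **B**, half-lives 0.1 h and 1 h: k = 6.931 and 0.693/h, giving w = 3.32 and 5.18.
- **C**, half-lives 0.1 h and 2 h: k = 6.931 and 0.347/h, giving w = 6.05 and 2.45.

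Example for A at minute 9: (1 − exp(−1.069 × 0.15)) / (1 − exp(−1.069 × 0.1667)) = 0.1482/0.1632 = 0.908.

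**3. Results, as a percentage of the true end-of-infusion concentration**

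| Profile | Draw at min 9 (footnote b only) | Draw at min 11 (both texts) | 5-min post-EOI sample | Mean over min 5–10 |
|---|---|---|---|---|
| A | 90.8 | 98 | 91.5 | 76 |
| B | 91.6 | 96 | 83 | 78 |
| C | 92.7 | 93 | 73 | 80 |

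A draw one minute early therefore understates C_EOI by 7 to 9%. A draw one minute late, which both texts allow, understates it by 2 to 7%.

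**4. Cmax.** With an early EOI draw, the observed maximum is the larger of the second and fourth columns: 91.5, 91.6 and 92.7%. On A the 5-minute sample becomes the maximum, so tmax moves there too. On B and C it gives no protection. With one exponential and slower decline it limits the loss: the observed maximum is 94.4% of true at a half-life of 1 h, 97.2% at 2 h and 98.6% at 4 h.

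**5. Clock.** On the SAP's clock the minute-9 sample has time 9 − 10 = −1 minute. On the protocol's start-of-infusion clock it has +9 minutes.

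**6. ECG, conditional.** If an EOI pair exists, and if the five-minute window stated for safety ECGs were used for it, the mean concentration during extraction would be 76 to 80% of C_EOI (last column).

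**The case against.** The row is specific and gives +1 in both its time and its PK cell, whereas the footnote is general. A careful site would follow the row. That is fair: a reader might infer that the protocol plainly permits sampling during the infusion, and it does not. It contradicts itself, and the row is probably what was meant.

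The size is also modest. The 7 to 9% is for a draw a full minute early, and on profile C the permitted late draw costs almost as much. A similar proportional error at every dose would move the intercept of the power model and leave the slope largely unchanged. Actual infusion and sample times are recorded and time deviations are listed, so early draws can be found afterwards. All this stands. It makes the defect small and detectable, but does not settle which window applies.

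On the ECG, a reader might go further and infer that the highest concentration in each participant is paired with a mistimed QTcF, creating a false lag that passes for a delayed QT effect. The documents do not support that:
- The ECG cell of the EOI row is blank in the text available. This proves little either way, since the 10- and 30-minute post-EOI rows are blank too although footnote e schedules ECGs there.
- The five-minute window is given for safety ECGs only.
- An ECG between the stop of infusion and a draw at +1 minute would comply with footnote d.
- Pairing rules may well be set in the separate plan, which is not available here.
- Neither document plans a check for delayed effect.
- Even if the five-minute window applied at every time point, the pooled linear slope on these profiles would fall by only about 3%.

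**Conclusion.** The conflict between the Table 2 row and footnote b is real and should be corrected. Its consequence is a C_EOI about 7 to 9% low for a draw one minute early, with a similar loss in Cmax on the matched profiles and a smaller one if decline is slower. Such a sample would also precede time zero on the SAP's clock. These percentages rest on the protocol's pre-study projection, on reading C0 and AUC(0-last) as intercept and total area, on an uninterrupted 10-minute infusion at constant rate, and on assumed half-lives for B and C. The contradiction itself rests on no assumption.

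The ECG point is secondary and conditional. Taking the ECG before the blood draw is not an error in itself. What is missing from these two documents is a limit at the one time point where concentration is rising, and it concerns an exploratory objective.

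**What to change.** 1. **Footnote b:** exempt the EOI sample from the ±1 minute window and state 0 to +1 minute after the infusion actually stops, as in the table row. Tying it to the actual stop also covers an infusion that overruns ten minutes. The 5-minute post-EOI row shows the same +1 against ±1 mismatch. It is harmless there, but can be aligned in the same edit.
2. **Separate concentration-QT plan:** state whether a Holter ECG is paired with the EOI sample and, if so, set its extraction window relative to the actual end of infusion.

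I would not replace C_EOI in that pair by a straight line from zero at infusion start to the EOI sample. With a sample at minute 11, such a line gives (7.5/11) × C(11), which is 0.785 to 0.874 of the true concentration at minute 7.5 on these profiles. That is 13 to 22% too low.

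The cost is one footnote edit and one sentence in a plan still to be written. No blood draw, ECG or visit is added. The site loses the minute before the end of infusion, and an early draw becomes a recorded deviation.

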2.0 INTRODUCTION

2.1 Study Rationale

The purpose of the study is to evaluate safety, tolerability, and pharmacokinetics (PK) of single, ascending doses of CS-1103, administered by intravenous (IV) infusion in healthy participants.

2.2 Background

[figure not shown]
There is an urgent need for a rapidly acting reversal agent for methamphetamine (meth) intoxication. Meth is the fastest growing drug of abuse in the U.S., representing nearly 800,000 annual emergency room visits,¹ with deaths increasing 14-fold since 2015 (32,856 deaths in 2021 alone),^{2,3} yet no current therapeutics are available for treating meth intoxication.

Clear Scientific is developing CS-1103 to treat acute toxic effects of meth. CS-1103 lowers the level of meth in the body by sequestering it in the central compartment, and accelerating its renal clearance into urine, therefore mitigating its toxic effects. [REDACTED]

[figure not shown]
Term	Percentage
GMOs	95
Organic	75
Natural	95
Artificial	85
Organic	65
Natural	95
Artificial	85
Organic	65
Natural	95
Artificial	85
Organic	65
Natural	95
Artificial	85
Organic	65
Natural	95
Artificial	85

■ [REDACTED]

Clear Scientific has completed a nonclinical program in compliance with guidelines published by the Food and Drug Administration (FDA).¹⁰ The results are summarized in the current Investigator's Brochure (IB).

The purpose of the planned Phase 1a clinical trial is to evaluate the safety, tolerability, and PK of CS-1103 following a single, ascending IV dose administration in healthy participants. The proposed route of administration in humans is IV.

2.3 Benefit/Risk Assessment

The benefit of the present study is that it will provide important human data on the safety, tolerability and PK of CS-1103, however there is no benefit to the healthy study participants. This study will provide a base of information for further development of this molecule, which has the potential to treat participants with meth intoxication. CS-1103 has been extensively evaluated in nonclinical studies. The development of hypersensitivity reactions in human participants is a potential risk. See [Section 2.2.1](#) for additional information. More detailed information about the known and anticipated benefits as well as the risks, and reasonably expected AEs of CS-1103 may be found in the current [IB](#).

For the justification of the starting dose and provisional dose range, see [Sections 4.3](#) and [4.5](#). A comprehensive set of safety assessments have been implemented (see [Section 8.2](#)) along with well-defined study stopping criteria (see [Section 4.6](#)) to ensure participant safety.

The Sponsor will immediately notify the Principal Investigator if any additional safety or toxicology information becomes available during the study.

This study will be performed in compliance with the protocol, International Council for Harmonisation of Technical Requirements for Pharmaceuticals for Human Use (ICH) Good Clinical Practice (GCP), and applicable regulatory requirements.

3.0 OBJECTIVES AND ENDPOINTS

Objectives	Endpoints
Primary 
 To assess the safety and tolerability of CS-1103, administered by IV infusion 	Standard safety and tolerability parameters but not limited to: 
 AE Vital signs (blood pressure, pulse rate, respiratory rate, oxygen saturation, and body temperature) Digital 12-lead ECGs/Holter Laboratory parameters (clinical chemistry, hematology, coagulation, urinalysis)
Secondary 
 To characterize the PK of CS-1103, administered by IV infusion 	Plasma and urine PK parameters including but not limited to 
 C_{max}, t_{max}, C_{EOI}, $AUC_{(0-last)}$, $AUC_{(0-inf)}$, $t_{1/2}$, λ_z, CL, V_{ss}, and V_z By-interval and cumulative CS-1103 excretion in urine (A_e and f_e) CL_r
Exploratory 
 To explore the relationship between CS-1103 plasma concentrations and changes in QT intervals during dosing, if any 	
 Concentration-QT correlation performed on baseline-corrected QTcF time-matched with PK. Concentration-QT correlation may be reported separately from the clinical study report

Abbreviations: AE = adverse event; A_e = amount; AUC = area under the concentration versus time curve; $AUC_{(0-inf)}$ = AUC from time zero extrapolated to infinity; $AUC_{(0-last)}$ = AUC from time zero to the last quantifiable concentration; C_{EOI} = concentration at the end of 10-minute IV infusion; CL = systematic clearance; CL_r = renal clearance; C_{max} = maximum concentration; ECG = electrocardiogram; F_e = fraction; IV = intravenous; λ_z = elimination rate constant; PK = pharmacokinetics; $t_{1/2}$ = half-life; QTcF = QT corrected for heart rate by Fridericia's formula; t_{max} = time to C_{max} ; V_{ss} = volume of distribution at steady-state following intravenous dosing; V_z = volume of distribution following intravenous dosing.

